Cellular phone communication. All participants will either be allowed to use their own personal cell phone for study communications or receive a cell phone with service through a nationwide cell phone service provider. If a participant chooses to use their personal cell phone for study communications and pays for text messages and/or phone calls on a per unit basis, we may reimburse the participant for the cost of those messages and calls made for this study. We have used study-provided cell phones to facilitate study communication previously (Athamneh et al., 2021, [name] et al., 2011).

BACtrack breathalyzer monitoring. The BACtrack breathalyzer (<https://www.bactrack.com>) contains a number of technological advances that make it ideally suited for remote breath samplings of alcohol use. To complete scheduled breathalyzer assessments, participants will log into the Remote Monitoring app on their smartphone, developed by the University of Kentucky. Participants will select to submit a breath sample and participants will simply blow into the device for a few seconds. The breathalyzer will be provided to the participants for the study. Participants will be able to keep their breathalyzer following completion of the study. If the breathalyzer is lost/stolen/damaged, the participant will be able to receive a new breathalyzer from the study team.

All participants will be asked to complete breathalyzer screens 3 times per day for approximately 35 days (approximately 7 days baseline, and approximately 28 days intervention). A period of approximately 28 days of the intervention was chosen to

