assessments; this may be on the same day as Session 1; the baseline monitoring phase will follow Session 2. During the baseline monitoring phase, participants will provide breath samples to assess for recent alcohol use and report their drinks per day and report their alcohol withdrawal symptoms per day. Following the baseline period, participants will return for Session 3, where they will undergo fMRI procedures and then be randomized to either the EFT or control group (Control Episodic Thinking, CET). Participants will complete 2 weeks of monitoring (Monitoring Phase 1) where they will provide three breath samples per day and report the number of drinks they consumed per day. Participants will then come back to the lab to generate new EFT/CET cues at Session 4, and then complete Monitoring Phase 2 for two more weeks. After conclusion of the second monitoring phase, participants will complete Session 5 which is composed of assessments and an fMRI scan. A one-month follow-up will be conducted as Session 6.

Episodic Future Thinking (EFT): Participants will generate positive future events they are looking forward to at a number of time points in the future (e.g., 1 day, 2 weeks, 1 month, 3 months, 1 year, 5 years, and 25 years).

Control Episodic Thinking (CET): Participants will generate positive recent past events that have happened to them at a number of time points (last night from 7pm-10pm, yesterday between 4pm-7pm, yesterday between 1pm-4pm, yesterday from 10am-12pm, yesterday between 7am-10am, the night before last between 7pm-10pm, and evening before last between 4pm-7pm).

Session 1	Session 2	Remote 7 days	Group Assignment	Session 3 fMRI	Remote 14 days	Session 4	Remote 14 days	Session 5 fMRI	Session 6 1 month later
-----------	-----------	---------------	------------------	----------------	----------------	-----------	----------------	----------------	-------------------------

Inclusion/exclusion

Inclusion criteria for signing consent will require that participants: (1) demonstrate high-risk or harmful drinking (AUDIT>15; i.e., 16 or higher), (2) be between 21-65 years old, and (3) have a desire to quit or cut down on their drinking, but do not have proximate plans to enroll in treatment for AUD during the study period.

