We will use a 3T Siemens MAGNETOM Prisma^{fit} scanner (Siemens, Erlangen, Germany) with a 20-channel head/neck coil. T1-weighted images will be acquired at $1 \times 1 \times 1 \text{ mm}^3$ resolution using 3D MPRAGE, FOV = $256 \times 256 \times 176 \text{ mm}^3$, TR/TE/TI = 1950/4.44/950 ms, FA = 12° , phase partial Fourier 7/8, slice partial Fourier 6/8, GRAPPA factor = 4 with 33 reference lines, and bandwidth = 140 Hz/pixel. Functional BOLD data will be acquired using EPI with thirty-three 4 mm interleaved slices with a 10% slice gap, TR/TE = 2000/30 ms, FA = 10° , in-plane resolution of $3.4 \times 3.4 \text{ mm}^2$, anterior-to-posterior phase encoding and a bandwidth = 2442 Hz/pixel. Participants will be instructed to keep their eyes open during the scan and direct their gaze on a white plus (+) sign centered on a black background.

Alcohol Consumption

Changes in drinks per day and the number of positive breath alcohol samples (BrAC) will be compared within subjects between pre-intervention and post-intervention. In

addition, differences in drinks per day and the number of positive BrAC samples will be compared between groups (EFT and CET). A Timeline Follow Back (TLFB⁴⁰) will be conducted during Session 2 (pre-intervention) and Session 6 (1-month follow-up) to assess the number of alcoholic drinks consumed daily for the past 30 days. During the intervention period (from Session 2 to Session 5), participants will report daily the number of alcoholic drinks consumed.

Alcohol Urges Questionnaire (AUQ)

The Alcohol Urges Questionnaire ⁴¹ will be used to assess craving for alcohol. This 8-question measure of drinking urges is scored by summing responses to a 7-point Likert scale. The dependent measure of the summed score will be compared within subjects between pre-intervention and post-intervention. In addition, differences in alcohol craving will be compared between groups (EFT and CET).

Alcohol Use Disorders Identification Test (AUDIT)

The Alcohol Use Disorders Identification Test (AUDIT⁴²) will be used to assess hazardous or harmful alcohol use. AUDIT is a 10-item screening tool that assesses alcohol consumption, drinking behaviors, and alcohol-related problems. Differences in alcohol AUDIT scores will be compared between groups (EFT and CET).

Alcohol Relative Reinforcement Schedule (ARRS)

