Objective 1: *We hypothesize that an intervention involving EFT will increase the temporal window and decrease alcohol valuation (consumption, demand, and craving).*

Our primary measure of alcohol use during the intervention period will be the daily self-reported number of drinks per day and the SOBERLINK breathalyzer screens. We will use generalized linear mixed models to compare the daily number of drinks between the EFT and CET groups. Mixed models is a method suited to the analysis of repeated measurement data. Here, the daily number of drinks will be modeled using a Poisson distribution. In the event the daily number of drinks exhibit over dispersion, other distributions, such as a negative binomial, will be considered. In a similar manner, dichotomous breathalyzer results data (positive or negative) throughout the 5-week field test will be analyzed as a function of intervention assignment, while accounting for time of day (morning, afternoon, evening) and repeated measures from each subject. Intrasubject correlation will be accounted for using an autoregressive correlation structure (AR(1)), since drinking days may be temporally related. In the event the AR(1) correlation structure is not representative of the data, other correlation structures will be considered. All missed assessments, although rare in our experience with similar field studies (approximately 5%), will be included as missing data. In the event of high rates of missing data, we will employ techniques consistent with the intention-to-treat paradigm, such as last observation carried forward methods or worst-case scenario (that all missing data is a positive BrAC measure).

Secondary analyses. In addition to the primary hypotheses listed above, we propose several additional analyses that will more fully characterize the behavior of our research participants and potentially lead to future research questions related to EFT in AUD. To this end, we hypothesize that EFT will result in changes (baseline versus post-intervention) in secondary outcome measures (e.g., Alcohol Withdrawal Symptoms Checklist). All these secondary hypotheses will be analyzed analogous to the primary hypothesis.

Covariate Plan:

We will test for individual differences in outcome measures for the intervention for each of these stratified variables. Therefore, we will include AUDIT score, SES, age, and gender in the analyses testing for an interaction between these variables and the intervention.

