Sensitivity Analyses:

Due to the longitudinal nature of the experimental design, some participant drop-out is expected. We will perform sensitivity analyses to identify and document any potential biases that may arise due to participant drop out.

- Attrition prior to randomization: We will evaluate if any demographics and assessment values from S1 are associated with participant drop-out at S2.
- Attrition between Session 3 and Session 4: We will evaluate if differences in the attrition rates between EFT and CET exist during the first 2-week field test. Moreover, we will evaluate if demographics and assessment values are associated with participant drop-out prior to S4.
- Attrition between Session 4 and Session 5: We will evaluate if differences in the attrition rates between EFT and CET exist during the second 2-week field test. Moreover, we will evaluate if demographics and assessment values are associated with participant drop-out prior to S5.
- Missing daily reports/BrAC during 4-week intervention: We will evaluate if there is an association between the percentage of missing data points during the 4-week intervention and average daily drinks to assess if missing data is missing at random. For example, a negative correlation between the average daily drinks and percentage missing data may suggest missing daily values are not random. In addition, we will evaluate if missing BrAC values are associated with time of day.
- Attrition at 1-month follow-up: We will evaluate if there are differences in the 1-month follow-up rates between the EFT and CET groups. We will evaluate if average daily consumption is associated with 1-month follow-up rates. We will evaluate if participant demographics and assessment values are associated with 1-month follow-up rates.

We will report the results of all germane sensitivity analyses in all publications and discuss potential biases that may result from participant drop-out.

Exploratory Analyses:

In addition, we will perform an exploratory mediation analysis evaluating if AUDIT score, SES, age, gender, psychiatric comorbidities, executive function, family history, impulsivity, and reward sensitivity mediate the relationship between intervention and the primary outcomes. This analysis will be completed using bootstrap-based approaches, as described in Preacher and Hayes.

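### The SAP's only breath-alcohol model spans five weeks, which takes in the week before randomisation; followed as written, it shrinks the EFT–CET risk difference to 28/35 = 0.80 of its value

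*SAP*

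**What the plan says.** The SAP has one model for the breath-alcohol (BrAC) results, under Statistical Analyses, Objective 1. Positive or negative results "throughout the 5-week field test will be analyzed as a function of intervention assignment, while accounting for time of day" and for repeated measures within a participant, with AR(1) as the default correlation structure. The Covariate Plan adds only AUDIT, SES, age and gender.

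The timing is set out elsewhere:
- Protocol 8.2 schedules breath samples three times a day for "approximately 35 days (approximately 7 days baseline, and approximately 28 days intervention".
- SAP, Study design, on the step that comes after baseline monitoring: "participants will return for Session 3, where they will undergo fMRI procedures and then be randomized to either the EFT or control group". The SAP's schematic also puts group assignment after the seven remote days.

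Other SAP text describes the window differently:
- The opening sentence of Objective 1 places its primary alcohol-use measure, daily drinks together with breathalyzer screens, in the intervention period.
- Sensitivity Analyses: "Missing daily reports/BrAC during 4-week intervention", with separate attrition checks for the first and the second two-week field test.
- Alcohol Consumption: "During the intervention period (from Session 2 to Session 5), participants will report daily the number of alcoholic drinks consumed".

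Some text points to a pre/post comparison. Protocol 4.1 and SAP, Alcohol Consumption, compare positive BrAC samples before and after intervention within participants, and separately between groups. Protocol 5.2 gives a mixed model with day, a pre/post term and group. The SAP's sample size rests on a group-by-time interaction. Protocol 14.1 bases its sample size on an ANCOVA that adjusts for the baseline measure.

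**The concern.** During the baseline week no one has been assigned, so EFT and CET cannot differ because of treatment. A model that contains assignment but no group-by-period term, fitted to all five weeks, averages that week's expected zero difference with the four weeks in which a difference can exist. The estimate is pulled toward no effect.

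The SAP also contradicts itself on the window. An analyst who takes the model sentence at its word gets a diluted estimate; one who takes the opening sentence of the same paragraph does not. A plan written in advance should not leave that choice open. It matters whether BrAC is part of the primary measure of alcohol use, as the SAP has it, or the secondary consumption measure, as Protocol 5.2 has it.

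A smaller, related gap is that neither the drinks model nor the BrAC model in Objective 1 names the baseline value of its outcome or the two balancing variables. That costs precision, not validity.

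**Working it through.** **Inputs from the documents.** 7 baseline days, 28 intervention days and 3 samples a day (Protocol 5.2 and 8.2); randomisation after the baseline week (SAP, Study design); no intervention during the baseline week (Protocol 8.2). The documents give no BrAC effect size, positive rate or correlation, so values for these below are assumptions.

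**What five weeks means.** 7 + 28 = 35 days = 5 weeks. The intervention alone is 14 + 14 = 28 days = 4 weeks. Only the first sum matches the model sentence.

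**Share of samples before assignment.** 7 × 3 = 21 of 35 × 3 = 105, or 20%.

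**Dilution on the risk-difference scale.** Let the true difference be 0 in the baseline week and δ, constant, in the 28 days, with equal completeness in both periods. The pooled difference is (7 × 0 + 28 × δ)/35 = 0.80δ.

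**Odds-ratio scale.** Let p0 be the control proportion positive and p1 the EFT proportion on intervention days. The pooled EFT proportion is 0.2·p0 + 0.8·p1. With p0 = 0.20 and a true odds ratio of 0.50:
- p1 = 0.125/1.125 = 0.111
- pooled proportion = 0.040 + 0.089 = 0.129, odds 0.148
- pooled odds ratio = 0.148/0.25 = 0.59

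At p0 = 0.50 the same steps give 0.58. A true odds ratio of 0.67 becomes about 0.73. Over p0 from 0.2 to 0.5 and odds ratios from 0.4 to 0.8, the log odds ratio is multiplied by 0.74 to 0.80.

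**AR(1) weighting.** Generalised least squares on 35 daily values gives these multipliers:

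| AR(1) correlation | 0 | 0.3 | 0.5 | 0.7 | 0.9 |
|---|---|---|---|---|---|
| Group effect, pooled | 0.80 | 0.79 | 0.78 | 0.77 | 0.70 |
| Same, with a pre/post main effect | 0.80 | 0.79 | 0.78 | 0.77 | 0.70 |

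The second row shows why a pre/post main effect is not enough: it removes the average change over time, but the group coefficient still averages both periods. In one large simulated data set (n = 3,000, odds ratio 0.50), the pooled-to-28-day ratio was 0.77 to 0.81 across independence GEE, exchangeable GEE and a random-intercept model, and 0.77 to 0.82 with the main effect added.

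**Unequal completeness.** With complete baseline data and 30% of intervention samples missing (assumed), the share is 19.6/26.6 = 0.74.

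**What the SAP's sample size implies.** Noncentrality = f²·N·m/(1 − ρ) = 0.0625 × 52 × 2/0.5 = 13, which gives power 0.818 at alpha 0.01. N = 50 gives 0.799, so 52 is reproduced. The calculation is for a group-by-time test, which the BrAC sentence does not contain.

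**Comparing the remedies.** Take equal variances and baseline-to-intervention correlation ρ (linear approximation, ρ assumed). Variance relative to 28 days unadjusted is 1 − ρ² for 28 days adjusted for baseline, and 2(1 − ρ) for the group-by-period contrast:

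| ρ | 28 days, adjusted | Group by period |
|---|---|---|
| 0.3 | 0.91 | 1.40 |
| 0.5 | 0.75 | 1.00 |
| 0.7 | 0.51 | 0.60 |

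Both remove the dilution. The adjusted 28-day model is the more precise at each value.

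**The case against.** The strongest reply is that nobody intends to pool. Protocol 4.1 and SAP, Alcohol Consumption, call for a pre/post comparison of BrAC; Protocol 5.2 has a pre/post term; the SAP's sample size assumes a group-by-time test; and Protocol 14.1 names a baseline-adjusted ANCOVA. On this view the five-week phrase is loose drafting and pooling is the least plausible reading.

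Much of that stands. It shows that a period contrast or baseline adjustment was probably in mind, and it rules out saying that the BrAC result will be diluted. It does not repair the model sentence. The pre/post comparison is described within participants, with the group comparison stated separately and without a window. Protocol 5.2 applies its model to the primary outcome measures, ranks BrAC as secondary and names no interaction. The two sample-size passages describe tests that Objective 1 does not carry over.

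A reader might also infer that daily drinks will be pooled, because the SAP runs the intervention period from Session 2. That sentence says when reports are collected. The drinks model has no five-week phrase, and its paragraph opens by referring to the intervention period. This is a labelling slip, not evidence of pooling.

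A reader might want the loss of power as one figure. The documents do not support one. The SAP's inputs belong to a different analysis, and nothing is given for BrAC, so none is offered here.

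**Conclusion.** The SAP's BrAC model is inconsistent about its window, and the sentence that specifies the model gives a biased estimate if followed. The risk difference is multiplied by 0.80, assuming a constant effect over 28 days, no expected baseline difference and equal completeness. AR(1) weighting or the log-odds scale gives about 0.70 to 0.80. The direction is toward no effect. Under no effect both periods have zero difference, so false positives are not inflated.

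The inconsistency is certain. The dilution is conditional on which sentence is followed. The absence of baseline and balancing covariates from Objective 1 is a lesser matter of precision, and Protocol 14.1 shows that baseline adjustment was contemplated.

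**What to change.** 1. In SAP Objective 1, replace the five-week phrase with the 28 post-randomisation days, Session 3 to Session 5. Adjust the BrAC model for the baseline-week proportion of positive samples, square-root baseline drinks per day and baseline ln(k). This agrees with the baseline-adjusted ANCOVA in Protocol 14.1.
2. Alternatively, keep all 35 days and state that group by period is the test. In that case do not also enter the baseline-week outcome as a covariate.
3. Adjust the drinks model for square-root baseline drinks per day and baseline ln(k). State which baseline drinks value was used at randomisation, since SAP, Randomization, does not say.
4. Align the Session 2 to Session 5 label under Alcohol Consumption with Objective 1 and Sensitivity Analyses.
5. In the Covariate Plan, stop describing AUDIT, SES, age and gender as stratified variables. SAP, Randomization, names drinks per day and baseline discounting as the balancing variables.

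These are wording changes, to be made before the between-group analysis. The trial already collects every variable needed. The price is two degrees of freedom in the drinks model and three in the BrAC model.

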14.0 Number of Subjects

14.1 Indicate the total number of subjects to be enrolled and how this number was determined (e.g., sample size calculation [show], number of available subjects in a finite pool, number of tests funding award would allow):

Although we have observed large effect sizes of EFT on DD in AUD participants in our preliminary studies (pre-post $d=1.6$; post-only $d = 0.68$), we used a more conservative medium effect size ($f= 0.25$) to inform sample sizes to increase power to detect effect on the broader range of measures proposed here (e.g., intensity of demand). Using the method proposed by Borm, Fransen, and Lemmens, and a pre- and post-measurement correlation of 0.70218, 76 total participants would be needed to complete this study (38 participants per group), assuming a type 1 error rate of 0.01 and 95% statistical power, based on an ANCOVA comparing the intervention while using the baseline measure as a fixed-effect covariate in the analysis.

We have been successfully recruiting individuals with AUD in our community for the past 8 years. Based on these 8 years of experience recruiting alcohol users into studies of comparable length and complexity, we anticipate that over 80% of consented participants will be eligible (i.e., randomized) and about 65% of those eligible individuals will complete this study. Thus, to achieve a final sample size of 76, we anticipate consenting 200 participants. We plan to enroll more than our average attrition rate because of the increased procedures and the time demands of the study.

14.2 If this is a multi-site study, indicate the number of subjects to be enrolled at this site and the total to be enrolled from all sites:

N/A

14.3 If applicable, indicate the number of potential subjects you expect to screen for enrollment, and the number of subjects you will need to complete the research procedures:

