Exclusion criteria include: (1) meeting moderate to severe DSM-5 criteria for substance-use disorders other than alcohol, nicotine, or marijuana, (2) having a current diagnosis of any psychotic disorder, (3) having a history of seizure disorders or traumatic brain injury, (4) having any contraindication for participation in the fMRI session, or (5) reporting current pregnancy or lactation.

Recruitment

Participants will be recruited from the community via posted flyers, word of mouth referrals, and electronic advertisements (e.g., Craigslist, Facebook). Participants may contact the lab directly via email, Facebook, phone, walk-in, face-to-face at tabling events, or completing the online pre-screening questionnaire. Participants will also be contacted directly if they have given prior permission (through previous informed consent form) or by completion of a confidential pre-screening questionnaire.

We have developed and are currently using a separate pre-screening protocol, which occurs prior to enrolling participants into our intervention protocols, to effectively decrease attrition in our studies by ensuring that participants meet most inclusion/exclusion criteria (e.g., MRI scanner eligibility) prior to enrolling into the randomized study. Given that this separate screening protocol is used for all currently on-going studies in the lab, we cannot accurately estimate the total number of potential participants we expect to screen. However, as described above, we expect enrolling 170 participants to complete 54. We plan to enroll more than our average attrition rate because of the increased screening procedures and the time demands of the study. Additionally, the first few participants enrolled into the study may be pilots.

Participant Retention

We will evaluate continuation in our study after a baseline period of drinking has been completed. We expect to retain 75% of our participants at this time point. Specifically, 75% of our participants will present with at least 4 out of 7 drinking days, and at least 4 days with 4 or more drinks or an average higher than 4 drinks per day on drinking days.

Once participants reach this study phase , we expect a 70% retention for the rest of the study.

Randomization

Participants will be randomly assigned to experimental or control groups, balanced by number of drinks per day (square root transformed) and baseline DD rates.

Sample size

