Although we have observed large effect sizes of EFT on DD in AUD participants in prior pilot studies (pre-post $d=1.6$; post-only $d = 0.68$), we used a more conservative medium effect size ($f=0.25$) to inform sample sizes and increase our power to detect effect on the broader range of measures proposed here (e.g., intensity of demand). Using a repeated measure correlation of 0.5, 52 total participants would be needed to complete this study (26 participants per group), assuming a Type I error rate of 0.01 and 80% statistical power, based on repeated measures within- between interaction ANOVA with 2 groups and 2 measurements.

Data Measures

Demographics

Demographic measures collected include age, sex, gender, ethnicity, and race.

SES

Education level, income, occupation/working status, household members

Delay discounting

To measure DD, the hyperbolic discounting model³⁸ will be fit to participants' indifference points across delays: $V=A/(1+kD)$ in which V is the immediate subjective value of the delayed option, A is its objective amount, D is its delay, and k is the only free parameter, indexing rate of discounting (larger k implies greater delay discounting, and a shorter temporal window). The discounting rate k will be log transformed to approach normality and stabilize the variance. Analysis will proceed by fitting the above equation to individual

subject data, then comparing values of discount rate $\ln(k)$ between experimental groups, as described above. We will compare fit to the hyperbolic model in comparison to alternative models as part of our third Objective.

Demand measures

To obtain dependent measures of demand, participants' data from the alcohol purchase task will be fit to a modified³⁹ exponential equation of the demand function¹⁸ to quantify the relationship between the price of alcohol and consumption: $Q=Q_0 \times 10^{k(\exp(-\alpha Q_0 C)-1)}$ where Q is consumption of the commodity, C is the price, Q_0 is the derived initial consumption without cost constraints (demand intensity), k is the span of the function in logarithmic units, and α is the demand elasticity. Values of k are set to a constant determined empirically by the actual data, leaving Q_0 and α as free parameters to be fit. Note that although the delay discounting model and the demand equations use k , they refer to different variables. Dependent measures will be compared between experimental groups, as described above.

Resting state fMRI

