The Alcohol Relative Reinforcement Schedule measures the extent to which alcohol serves as a reinforcer for an individual compared to other activities or substances⁴³. Participants will be asked to rate the frequency with which they engage in activities with and without alcohol and how enjoyable those activities are. Changes in alcohol reinforcing value before and after the intervention will be compared between groups (EFT and CET).

Alcohol Withdrawal Symptoms

The Alcohol Withdrawal Scale (AWSC⁴⁴) will be used to assess the severity of alcohol withdrawal symptoms. The AWS consists of a list of common withdrawal symptoms

associated with alcohol cessation, including physical and psychological manifestations. This is a 17-question where the withdrawal symptoms are scored by summing responses to a 5-point Likert scale. Severity of withdrawal symptoms will be compared between groups (EFT and CET).

Contemplation Ladder

The Contemplation Ladder is a 10-point scale that assesses readiness to change alcohol use. Changes in readiness to change alcohol before and after the intervention will be compared between groups (EFT and CET).

Penn Alcohol Craving Scale

The Penn Alcohol Craving Scale (PACS⁴⁵) is a 5-item questionnaire that measures an individual's craving to drink alcohol in the past week. Changes in alcohol craving before and after the intervention will be compared between groups (EFT and CET).

Statistical Principles

Data preparation and analysis occurs in 3 steps: (1) assessment of data integrity; (2) descriptive analyses; and (3) longitudinal analyses. To assess data integrity, the distribution of all variables will be examined, appropriate methods will be used for handling missing data, and distributional transformations will be applied if needed to meet normality assumptions. We will also evaluate data for, and report the results of, overall consistency (e.g., between self-reported use and breath sample results). A significance level of $p<0.05$ will be used for all analyses. Multiple testing corrections will be used to control for false positives. Here we present our current analysis plan for the proposed tests. We recognize that upon completion of data collection, we may identify additional hypotheses to test. We will first implement the analysis plan proposed herein, followed by additional hypotheses and analyses as secondary/explorative thereafter.

Statistical Analyses

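### The SAP's fallback for high missing-data rates has no threshold, choice rule or stated role; if all-positive coding replaced the mixed model, it would weaken or distort the BrAC comparison

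*SAP*

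**What the plan says.** The SAP (Statistical Analyses, Objective 1) analyses daily drinks and dichotomous breathalyzer results with mixed models. BrAC results "throughout the 5-week field test will be analyzed as a function of intervention assignment", allowing for time of day and repeated measures.

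The default for gaps is: "All missed assessments, although rare in our experience with similar field studies (approximately 5%), will be included as missing data". The fallback follows: "In the event of high rates of missing data, we will employ techniques consistent with the intention-to-treat paradigm", with the examples "such as last observation carried forward methods or worst-case scenario (that all missing data is a positive BrAC measure". Statistical Principles adds only that "appropriate methods will be used for handling missing data".

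On expected loss, SAP Participant Retention says that after the baseline phase "we expect a 70% retention for the rest of the study". Protocol 14.1 expects that "about 65% of those eligible individuals will complete this study", where eligible means randomised.

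The SAP's Sensitivity Analyses compare attrition between arms, relate missingness to drinking and time of day, and promise to report and discuss possible bias. They neither list the fallback nor tie any check to it.

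BrAC is a primary measure of alcohol use in SAP Objective 1 and the secondary measure of consumption in Protocol 5.2.

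**The concern.** Three things are left open: what rate counts as high (and whether it is judged by sample, person or arm), which method is then used, and whether it replaces the mixed model or sits beside it. The choice could therefore be made after the missing rates in each arm are known.

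The choice matters because coding every missed sample positive is a worst case for the positive rate, not for the comparison of arms. It pulls both arms towards 100% and makes the result depend partly on who left. A real EFT effect on BrAC could be missed, or a spurious difference could appear in either direction.

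**Working it through.** **The plan's own figure.** The SAP states that "52 total participants would be needed to complete this study (26 participants per group", for f = 0.25, correlation 0.5, alpha 0.01 and 80% power. With noncentrality f²·N·2/(1−0.5) = 0.0625 × 52 × 2/0.5 = 13.0 on 1 and 50 df, power is 0.818; N = 50 gives 0.799. So 52 reproduces. It says nothing about BrAC and serves here only to set the number per arm.

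**Number per arm.** 52/0.70 ≈ 74, or 37 per arm. Other readings give more: 170 × 0.75 ≈ 127, or 63 per arm (SAP Recruitment and Participant Retention), and 76/0.65 ≈ 117, or about 58 per arm (Protocol 14.1).

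**Missing share.** The documents do not give the timing of loss. Assume even loss over T days after randomisation, with T = 28 (the field period) or T = 58 (28 days plus about 30 to Session 6), and 5% intermittent misses. Let L = drop-out × 28/T. Then m = L/2 + 0.05(1 − L/2).

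- Drop-out 30%: m = 11.9% (T = 58) or 19.3% (T = 28).
- Drop-out 35%: 13.0% or 21.6%. Drop-out 25%: 10.7% or 16.9%.
- Extremes at 30%: 5% if everyone leaves after day 28; 0.30 + 0.05 × 0.70 = 33.5% if everyone leaves at the start.
- Over the SAP's 35 days at 30%: (7 × 0.05 + 28m)/35 = 10.5% to 16.4%.

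**Effect of all-positive coding.** An observed rate p becomes p(1−m) + m.

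- Equal m: a true difference is multiplied by (1−m), here 0.88 or 0.81. People who leave early are scored as nearly all positive, which adds variation between people.
- Unequal m, no true effect: the false difference is (m2−m1)(1−p). At p = 0.30 and drop-out 35% v 25%, it is (0.130−0.107) × 0.70 = 0.016 or (0.216−0.169) × 0.70 = 0.033.
- Let q be the positive rate among missed samples. The bias of a single arm's rate is m(1−q) with all-positive coding and m(q−p) in size with observed data. All-positive coding is nearer the truth only if q > (1+p)/2: 65% at p = 0.30, 75% at p = 0.50.

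**Power, equal 30% loss.** Simulation with 37 per arm, 84 samples each (3 per day × 28), logit-normal person effects, loss unrelated to drinking, cluster-robust pooled logit and two-sided 5%. Entries are observed data / all-positive coding, in %.

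| Positive rates | SD 0.8, T=58 | SD 0.8, T=28 | SD 1.2, T=58 | SD 1.2, T=28 |
|---|---|---|---|---|
| 25% v 35% | 74/47 | 72/30 | 51/36 | 48/25 |
| 50% v 60% | 63/52 | 61/42 | 43/37 | 39/30 |
| 65% v 75% | 74/67 | 73/59 | 50/47 | 48/43 |

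A random-intercept logistic model at 25% v 35% gives 77.5/45.3, 75.3/31.2, 54.3/36.3 and 54.6/24.7. If people with more positive samples leave more often, by the same rule in both arms, it gives 77.0/53.6, 74.6/45.2, 53.4/41.2 and 52.6/37.2. Across all models and SDs run, the fall is roughly 11 to 44 points at 25% v 35%, 5 to 19 at 50% v 60% and 3 to 16 at 65% v 75%. With 63 per arm at 25% v 35% and SD 0.8, power goes from 91–93% to 48–67%.

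**No true effect.** With drop-out of 35% v 25%, all-positive coding rejects in about 5% to 10% of trials. With 40% v 20%, it rejects in about 5% to 24%. With equal loss it stays at about 5% to 7%. Observed data reject in 4.8% to 5.5% at 30% positive.

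**The case against.** **The fallback may never be used.** The design works against missing samples. Protocol 8.2 requires drinking reports on 5 of 7 baseline days, replaces lost breathalyzers and pays for each sample whatever its result; Protocol 15.4 adds a bonus for complete days. This stands as mitigation, but it limits missed samples among people still in the study. It does not prevent the 30% to 35% loss that the documents themselves expect.

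**The 5% figure.** A reader might infer that 5% contradicts 70% retention. It need not: 5% can describe misses among people who remain.

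**The harm may be small.** This stands in part. The documents give no positive rate, and at high rates the power loss is a few points. The low end of the rejection range for 35% v 25% drop-out is close to nominal. No document predicts unequal loss.

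**All-positive coding might be right.** It would be if nearly all missed samples were positive. The SAP gives no evidence for that, and its adjustment for time of day suggests that positivity is expected to vary over the day.

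**The SAP already examines attrition.** It does, and it commits to discussing bias. But these checks do not re-estimate the effect. A correlation between missingness and observed drinking can describe missingness; it cannot show that data are missing at random.

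**Conclusion.** The gap in the text is certain: no threshold, no choice between methods, no stated role. The direction of the harm follows from arithmetic. Its size rests on assumed positive rates, between-person SD, and timing and split of loss, and it ranges from slight to large.

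Some stronger readings are tempting and are not supported:

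- That the SAP has decided to replace its main analysis with all-positive coding. It leaves this open, and the harm arises only if the fallback is both triggered and used as a replacement.
- That the fallback generally inflates type I error. With equal loss it stays near nominal, and no inflation is shown for LOCF.
- That all primary outcomes are affected. The all-positive rule applies to BrAC only, whose status differs between the two documents; self-reported drinks, delay discounting, demand and craving are outside it.

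The sponsor should change this wording, but it is no more than a should-fix point.

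**What to change.** In SAP Objective 1, replace the fallback sentence with two statements:

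- The likelihood-based mixed model on all observed assessments from randomised participants is the main analysis, whatever the rate of missing data.
- LOCF, if kept, and all-missing-positive for BrAC are labelled sensitivity analyses, reported with the missing share in each arm.

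Optional: because the main model still relies on missing at random, add a graded analysis with arm-specific departures from it (delta-adjusted imputation is one way). In Sensitivity Analyses, describe the correlation check as characterising missingness.

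The cost is SAP wording and a little programming, with no new data collection.
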